4.2 Design Diagram

This is a Phase 3, randomized, double-blind, placebo controlled, multicenter study of adalimumab in anti-TNF naïve Chinese subjects with moderately to severely active CD ($220 \leq \text{CDAI} \leq 450$) and elevated hs-CRP ($\geq 3 \text{ mg/L}$). The study consists of an 8-week DB period followed by an OL period of 18 weeks. Subjects will be randomized in a 1:1 ratio to receive adalimumab or placebo at Baseline. Subjects randomized to adalimumab at Week 0 will receive blinded adalimumab 160 mg at Week 0, 80 mg at Week 2, and 40 mg at Week 4 and Week 6. Subjects randomized to placebo at Week 0 will receive blinded placebo at Week 0 and Week 2, then will receive blinded adalimumab 160 mg at Week 4 and 80 mg at Week 6. At Week 8, all subjects will enroll in an 18-week OL period to receive adalimumab 40 mg every other week (eow). No drug will be administered at the final study visit.

The study was designed to enroll approximately 200 subjects to meet scientific and regulatory objectives without enrolling an undue number of subjects in alignment with ethical considerations.

[figure not shown]
The study duration will be up to 39 weeks, and will include a screening period of up to 35 days, an 8-week double blind treatment period, an 18-week OL period and a 70-day follow-up period. All subjects will have a follow-up phone call approximately 70 days after the last administration of study drug to obtain information on any new or ongoing AEs. The 70-day follow-up phone call will not be required for any subject who initiates adalimumab therapy not supplied in the context of Study M14-233 after the end of study participation.

At or after Week 12, any subject who experiences inadequate response may increase dose to OL adalimumab 80 mg eow. If the subject has received OL 80 mg eow therapy and continues to demonstrate inadequate response, he or she should be withdrawn from the study per PI discretion.

Subjects may discontinue adalimumab treatment at any time during study participation. Subjects who end study participation early will have a Premature Discontinuation Visit.

A schematic of the study design is shown in [Figure 1](#).

Figure 1. Study Design

The study activities are presented in [Table 1](#).

Table 1. Study Activities

Activity	Screening (35 Days)	Day -21 ^a	Day -7 ^a	Baseline (Wk 0) ^b	Wk 2	Wk 4	Wk 6	Wk 8	Wk 10	Wk 12	Wk 14	Wk 16	Wk 18	Wk 20	Wk 22	Wk 24	Wk 26/ Premature Discontinuation	Unscheduled Visit	70-Day Follow-Up Call ^c

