6.0 Analysis Conventions

Definition of Baseline

The Baseline Visit date is the date when the first dose of study drug is received and referred to as Day 1 or Week 0. The baseline value for a variable is defined as the last non-missing value on or before the date of the first dose of study drug.

When analyzing laboratory parameters and vital signs on the Any Adalimumab analysis set, the Baseline Visit date is the date when the first dose of adalimumab is received and will be counted as Day 1 or Week 0. The baseline value for a laboratory or vital sign measurement is defined as the last non-missing value on or before the date of the first dose of adalimumab.

Definition of Final Observation

Final observation in the 4-week DB placebo controlled treatment period is defined as the last non-missing observation collected within 70 days following the last dose of study drug or the date subjects initiate adalimumab therapy not supplied in the context of Study M14-233 for subjects who discontinue the study before Week 6, and on or before the day of the first dose of study drug at Week 6 for subjects who continues the study.

Final observation in the DB/OL period for the Any Adalimumab set is defined as the last non-missing observation collected within 70 days following the last dose of study drug, or the date subjects initiate adalimumab therapy not supplied in the context of Study M14-233.

Definition of Rx Days (Days Relative to the First Dose of Study Drug)

Rx Days are calculated for each time point of interest and provide a quantitative measure of days between the event and Day 1 (which can be the day of the first dose of study drug or the day of the first dose of adalimumab, depending on the analysis). That is, the Rx Day is calculated as the event date minus Day 1 plus 1. The Rx Day will be a negative value when the time point of interest is prior to Day 1, and the Rx Day will be a positive

value when the time point of interest is after Day 1. By this calculation algorithm, the first dose day is Rx Day 1, while the day prior to the date of first dose is defined as Rx Day –1 (there is no Rx Day 0). Rx Days are used to map actual study visits to the protocol-specified study visits.

Definition of Analysis Windows

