Since subjects do not always adhere to the study visit schedule, the following rules will be applied to assign actual visits to protocol-specified visits including early termination visits. For each study visit mentioned in the protocol, a nominal or target day will be selected to represent the corresponding visit along with a window around the target day. Windows will be selected in a non-overlapping fashion so that a date collected on the CRF does not correspond to multiple visit windows. Moreover, windows will not discard any post-baseline measurement recorded on the CRF. If a subject had two or more actual visits in one visit window, the visit closest to the target will be used as the study visit for that window. If two visits are equidistant from the target, then the later visit will be used for reporting. For efficacy related analyses, if multiple measurements for a particular parameter are collected on the same day for the same subject, the average of those measurements will be used. For safety related analyses, if multiple measurements are made for a particular laboratory or vital sign parameter on the same day for the same subject, the average of the values will be used in the analyses. For summaries and listings of shift from baseline and potentially clinically significant values all values will be considered in the analyses.

Table 2. Visit Windows for Analysis of CDAI and Vital Sign

Scheduled Week	Nominal Day	Time Window (Rx Day A Range)
Week 0 DB	1 ^a	≤ 1
Week 2 DB	15	2 – 22
Week 4 DB	29	23 – 36
Week 6 DB	43	37 – 50
Week 8 DB	57	51 – 64 ^b
Week 10 OL	71	65 ^c – 78
Week 12 OL	85	79 – 92
Week 14 OL	99	93 – 106
Week 16 OL	113	107 – 120
Week 18 OL	127	121 – 134
Week 20 OL	141	135 – 148
Week 22 OL	155	149 – 162
Week 24 OL	169	163 – 176
Week 26 OL	183	177 – 190

Rx Day A = date of visit – date of first study drug injection in double-blind treatment period + 1

- a. Date of first study drug injection in double-blind treatment period.
- b. For Week 8 DB, visit window was from Rx Day 51 to Rx Day 64 or the date of the first injection in OL period (if applicable), whichever comes first.
- c. For Week 10 OL, visit window was from Rx Day 65 or the date of the first injection in OL period + 1 (if applicable), whichever comes first, to Rx Day 78.

Table 3. Visit Windows for Analysis of hs-CRP, Chemistry and Hematology

Scheduled Week	Nominal Day	Time Window (Rx Day A Range)
Week 0 DB	1 ^a	≤ 1
Week 2 DB	15	2 – 22
Week 4 DB	29	23 – 36
Week 6 DB	43	37 – 50

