Week 22	155	149 – 162
Week 24	169	163 – 176
Week 26	183	177 – 190

Rx Day B = date of visit – date of first dose of adalimumab + 1

- a. Date of first dose of adalimumab in double-blind treatment period.

Table 7. Visit Windows for Analysis of hs-CRP, Chemistry and Hematology (Any Adalimumab)

Visit Week	Nominal Day	Time Window (Rx Day B Range)
Week 0	1 ^a	≤ 1
Week 2	15	2 – 22
Week 4	29	23 – 36
Week 6	43	37 – 50
Week 8	57	51 – 71
Week 12	85	72 – 99
Week 16	113	100 – 127
Week 20	141	128 – 162
Week 26	183	163 – 190

Rx Day B = date of visit – date of first dose of adalimumab + 1

a. Date of first dose of adalimumab in double-blind treatment period.

Table 8. Visit Windows for Analysis of Urinalysis (Any Adalimumab)

Visit Week	Nominal Day	Time Window (Rx Day B Range)
Week 0	1 ^a	≤ 1
Week 4	29	2 – 43
Week 8	57	44 – 71
Week 12	85	72 – 112
Week 20	141	113 – 161
Week 26	183	162 – 190

Rx Day B = date of visit – date of first dose of adalimumab + 1

a. Date of first dose of adalimumab in double-blind treatment period.

Table 9. Visit Windows for Analysis of Fecal Calprotectin and IBDQ (Any Adalimumab)

Visit Week	Nominal Day	Time Window (Rx Day B Range)
Week 0	1 ^a	≤ 1
Week 4	29	2 – 43
Week 8	57	44 – 71
Week 26	183	72 – 190

Rx Day B = date of visit – date of first dose of adalimumab + 1

a. Date of first dose of adalimumab in double-blind treatment period.

Definition of Missing Data Imputation

The following imputation methods will be used to impute missing values in the efficacy analyses. In addition, an observed case analysis will be performed.

Non-Responder Imputation (NRI)

The NRI approach is used for binary efficacy variables. These variables can take values of 'Achieved' or 'Not Achieved' or may be missing for any reason including discontinuation from study. According to the NRI imputation approach, all missing value will be considered as 'Not Achieved.'

Subjects who dose-escalate from OL adalimumab 40 mg eow to OL adalimumab 80 mg eow due to disease flare or non-response will be imputed as 'Not Achieved' in the analysis of binary efficacy variables.

For the analysis of Week 26 efficacy variables only for dose-escalated subjects, the remission/response status will be determined based on the observed data at Week 26 after the dose escalation.

Last Observation Carried Forward (LOCF)

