- Number and percent of subjects by treatment group and by investigator and/or site number in DB and OL periods
- Number and percent of subjects completing the DB Week 0 – 4, Week 0 – 8 and OL Week 8 – 26, and discontinuing during the DB Week 0 – 4, Week 0 – 8 and OL Week 8 – 26 visits, respectively
- Subject disposition, including the number and percent of subjects who prematurely discontinued during the DB Week 0 – 4, 0 – 8, and OL Week 8 – 26, respectively, by primary reason and by any reason

Summary of protocol deviations will be provided.

9.0**Study Drug Exposure and Compliance**

Study drug exposure and compliance will be summarized using the mean, standard deviation, minimum, median, and maximum. Exposure to study drug (total patient years) will be summarized for each treatment group using Safety Analysis Set.

- Total exposure for DB placebo controlled period = date of Week 4 injection – date of first study drug dose, for subjects who did not prematurely discontinue before Week 4; If a subject discontinued at or before Week 4, then exposure is defined as "date of last injection prior to Week 4 – date of first injection + 14 days or the date subjects initiate adalimumab therapy not supplied in the context of Study M14-233, whichever comes first."

The number of injections received at each schedule time point will be summarized with number and percent for each treatment group using Safety Analysis Set.

Compliance (%) is defined as the number of injections received divided by the number of injections planned (rounded to 0.1) during the subject's participation in Study M14-233 and multiplied by 100 (rounded to 0.1%). Treatment Compliance will be summarized for the safety analysis set using descriptive statistics. Subjects with missing data for the number of injections returned will be excluded from the summary.

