11.0 Safety Analysis

11.1 General Considerations

Safety analyses will include reporting of adverse events, laboratory, and vital sign measurements. Safety analyses will be carried out using the Safety set for the DB placebo controlled period (Week 0 to Week 4), and will be carried out using the Any Adalimumab set for the DB/OL period of Any Adalimumab (the entire study on or after the first dose of adalimumab up to 70 days after the last dose of adalimumab, or the date subjects initiate adalimumab therapy not supplied in the context of Study M14-233). The safety analyses results through Week 4 will be presented using two treatment groups (i.e., ADA160/80 versus placebo). The safety analysis on the Any Adalimumab set will be presented for all the subjects as one adalimumab treatment group.

Comparisons between active treatment and placebo groups will be performed for the DB placebo controlled period using the safety analysis set. The safety variable will be summarized by treatment according to the treatment a subject actually received. The differences between treatment group and placebo in safety parameters will be evaluated using two-sided tests at the significance level of 0.100.

For the any adalimumab analysis Set, only summary statistics will be provided for adalimumab treatment.

Missing safety data will not be imputed.

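### SAP 6.0 runs the final observation of the four-week placebo-controlled period to the Week 6 dose, two weeks after placebo subjects start adalimumab

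*SAP*

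**What the plan says.** SAP 6.0 (Definition of Final Observation) gives two rules for the placebo-controlled period, which it describes as lasting four weeks.

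- Subjects who continue: the last value "on or before the day of the first dose of study drug at Week 6 for subjects who continues the study".
- Early leavers, that is, the rule "for subjects who discontinue the study before Week 6": the last value within 70 days of the last dose, or up to the start of non-study adalimumab.

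SAP 4.2 states that subjects randomized to placebo receive placebo at Weeks 0 and 2, "then will receive blinded adalimumab 160 mg at Week 4 and 80 mg at Week 6".

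Elsewhere the SAP ends the same period at Week 4. SAP 9.0 has "Total exposure for DB placebo controlled period = date of Week 4 injection", less the date of first dose. SAP 10.3 compares arms over time from Week 0 to Week 4. SAP 11.1 presents safety through Week 4 as the 160/80 mg arm against placebo. SAP 11.2.1 closes the adverse event window at the Week 4 dose and allows the 70-day tail only to subjects who left before Week 4. SAP 12.1 gives the reason for the split: placebo subjects start adalimumab induction at Week 4. Nothing in either document explains a Week 6 cut-off.

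**The concern.** SAP 11.3 asks for shift tables from baseline to final value for hematology and chemistry, and SAP 11.3.1 asks for the same for liver tests. Neither names the period or the columns. SAP 6.0 holds the only specific definition of a final value for the placebo-controlled period, so a programmer building these tables by arm would use it. Any Week 6 sample from a continuing placebo subject would then stand as that subject's end-of-placebo value, although it was drawn after 160 mg of adalimumab.

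The visit windows do not prevent this, because SAP 6.0 says that shift summaries consider all values. At stake is whether these descriptive tables can be read as a placebo-controlled comparison. The active arm's final value also moves past its Week 4 dose, but that arm is on adalimumab throughout.

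**Working it through.** **1. Boundaries side by side**

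| Use | Place | End of placebo-controlled period |
|---|---|---|
| Exposure | SAP 9.0 | Week 4 injection |
| Efficacy over time | SAP 10.3 | Week 4 |
| Safety reporting | SAP 11.1, 12.1 | Week 4 |
| Treatment-emergent events | SAP 11.2.1 | Week 4 dose; 70-day tail only if discontinued before Week 4 |
| Final observation | SAP 6.0 | Week 6 dose; 70-day tail if discontinued before Week 6 |

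**2. Length of the period.** Nominal days from SAP Tables 2 and 3: Week 0 = Day 1, Week 4 = Day 29, Week 6 = Day 43.

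- Exposure rule: 29 − 1 = 28 days.
- Final-observation rule: 43 − 1 = 42 days.
- Excess: 42 − 28 = 14 days, or 14/42 = one third of the longer window. In the placebo arm all of it follows the first adalimumab dose.

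**3. Time from first adalimumab dose to a Week 6 sample, placebo arm.** The visit tolerance is ±3 days (note b to the study activities table). Week 4 is then Day 26 to 32 and Week 6 is Day 40 to 46.

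- Nominal: 43 − 29 = 14 days.
- Minimum: 40 − 32 = 8 days.
- Maximum: 46 − 26 = 20 days.

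Days 40 to 46 lie in the Week 6 window of SAP Table 3 (37 to 50), not in the Week 4 window (23 to 36).

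**4. Early-stop clause.** A placebo subject who takes the Week 4 dose and leaves before Week 6 may contribute a value up to Day 29 + 70 = Day 99. SAP 11.2.1 would not give this subject the tail.

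**5. Are Week 6 samples drawn?**

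- For: SAP Table 3 has a Week 6 window for hs-CRP, chemistry and hematology. Protocol Table 1 marks chemistry and hematology at Week 6. The hematocrit table in Protocol 5.3.1.1 uses the Week 6 value for the Week 8 CDAI.
- Against: the Protocol synopsis lists these tests at Screening and Weeks 0, 2, 4 and 8 in the double-blind period, without Week 6.

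The number of placebo subjects affected is therefore at most about 100, the planned arm size. If sites followed the synopsis, it is only those with unscheduled samples.

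**The case against.** The strongest reply is that SAP 11.1 already confines the two-arm safety outputs to Week 0 through Week 4. On that reading the last value up to Week 4 is used, and only the wording of SAP 6.0 is wrong. This partly stands: SAP 11.3 and 11.3.1 name no period, so the effect on the tables is an inference. But SAP 11.1 is a general statement and SAP 6.0 is the specific definition of final. A programmer would have to choose between them, and on either reading SAP 6.0 needs correcting.

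The evidence for Week 6 samples is also uneven. A visit window is not a collection schedule, the hematocrit table speaks only to hematocrit, and Protocol Table 1 and the synopsis disagree. The effect must therefore stay conditional on a sample having been taken.

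The 70-day clause has little practical weight. Protocol 5.4.1 places the discontinuation visit within two weeks of the last dose, and later contact is by telephone.

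A reader might infer three stronger points that the documents do not support.

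- **Contamination of efficacy, adverse event or other safety results.** The primary endpoint has its own Week 4 window and non-responder imputation. By-visit laboratory comparisons, exposure and treatment-emergent events do not use this definition. Maximum-shift and Grade 3 or higher outputs have no competing definition, and SAP 11.1 limits their two-arm versions to Week 4.
- **A second error in the Any Adalimumab tables.** There, baseline is "defined as the last non-missing value on or before the date of the first dose of adalimumab", so a placebo-arm Week 6 sample is day 9 to 21 on that clock (the gap plus 1) and falls in the Week 2 window of SAP Table 7 (2 to 22). The two sets use different clocks by design, and a sample may properly appear in both. The fault lies only in labelling it as placebo-controlled.
- **A bias in a known direction.** The documents give no basis for saying whether the tables would favour or disfavour adalimumab.

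**Conclusion.** The contradiction is certain: SAP 6.0 ends the period at the Week 6 dose and every other SAP boundary is Week 4. The consequence is conditional. It requires that the baseline-to-final hematology, chemistry and liver shift tables are shown by arm, as SAP 11.1 implies, that SAP 6.0 is followed as written, and that a Week 6 sample exists. Under those assumptions a continuing placebo subject's final value is an on-adalimumab value, and these tables do not give a placebo-controlled comparison. Because the tables are descriptive and no efficacy conclusion depends on them, this is a minor point.

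**What to change.** - In SAP 6.0, define the final observation of this period as the last non-missing value on or before the day of the first study drug injection given at or after the Week 4 visit.
- Apply the 70-day tail, or the date non-study adalimumab starts, only to subjects who discontinue without receiving any such injection.
- Align the boundary wording in SAP 9.0 and 11.2.1 with this. They now differ on a subject who discontinues at Week 4.
- State in SAP 11.3 and 11.3.1 which period and columns the shift tables use.

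Replacing Week 6 by Week 4 in the present sentence would not be enough. It would leave unclear a subject withdrawn at the Week 4 visit without a dose, and a subject who misses the Week 4 dose but stays in the study. The wording above places both.

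The cost is SAP wording and programming; no data collection changes. Same-day Week 4 values are kept, and Protocol 5.3.1.1 has blood drawn before dosing whenever possible. A sample drawn after the Week 4 injection but inside the Week 4 window, which runs to Day 36, would leave the final value yet remain eligible for the by-visit Week 4 summary. The SAP should say so.

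Separately, the synopsis laboratory schedule, Protocol Table 1 and the hematocrit table in Protocol 5.3.1.1 must be reconciled on whether Week 6 samples are drawn.

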During the OL period, in addition to the TB screening described above, laboratory tests (hematologic and chemical analysis, including hs-CRP) will be performed during study visits at Weeks 12, 16, 20, and 26/Premature Discontinuation, and urinalysis will be performed at Weeks 12, 20, and 26/Premature Discontinuation.

AEs will be collected during the study and for 70 days after the last study drug administration.

Crohn's Disease Activity Index (CDAI) will be obtained during the Screening Period and at Weeks 0, 2, 4, 6, 8, 12, 16, 20, and 26/Premature Discontinuation. If the subject doses onsite then the CDAI will also be completed at Weeks 10, 14, 18, 22, and 24. The inflammatory bowel disease questionnaire (IDBQ) will be administered at Weeks 0, 4, 8, and 26/PD.

Subjects should adhere to the required visit schedule. Study visits should occur within the ± 3 day visit window. The Baseline visit at Week 0 should occur within 35 days of the Screening visit.

Diagnosis and Main Criteria for Inclusion/Exclusion:

Main Inclusion:

1. Male or female of Chinese descent with full Chinese parentage 18 to 70 years (inclusive) of age at Baseline (Week 0).
2. Confirmed diagnosis of Crohn's disease for at least 3 months prior to Baseline (Week 0). Appropriate documentation of biopsy results consistent with the diagnosis of CD, in the assessment of the Investigator, must be available.
3. Subject has hs-CRP ≥ 3 mg/L in all laboratory measurements during the Screening Period.
4. Crohn's Disease Activity Index (CDAI) ≥ 220 and ≤ 450 at Baseline (Week 0) despite concurrent or prior treatment with an adequate course, in the opinion of the investigator, of at least one of the following (oral corticosteroids or immunosuppressants or both as defined below):
 - Subjects taking oral corticosteroids, excluding budesonide:
 - Oral corticosteroid dose must be ≤ 20 mg/day (prednisone or equivalent);
 - For subjects with a dose > 10 and ≤ 20 mg/day, dose has been stable for at least 7 days prior to Baseline and the duration of the current steroid course has been at least 14 days prior to Baseline.
 - For subjects with a dose ≤ 10 mg/day, dose has been stable for at least 10 days prior to Baseline (Week 0) and the duration of the current steroid course has been at least 14 days prior to Baseline (Week 0).
 - Subjects taking oral budesonide:
 - Dose must not exceed 9 mg/day;

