Week 8 DB	57	51 – 71 ^b
Week 12 OL	85	72 ^c – 99
Week 16 OL	113	100 – 127
Week 20 OL	141	128 – 162
Week 26 OL	183	163 – 190

Rx Day A = date of visit – date of first study drug injection in double-blind treatment period + 1

- a. Date of first study drug injection in double-blind treatment period.
- b. For Week 8 DB, visit window was from Rx Day 51 to Rx Day 71 or the date of the first injection in OL period (if applicable), whichever comes first.
- c. For Week 12 OL, visit window was from Rx Day 72 or the date of the first injection in OL period + 1 (if applicable), whichever comes first, to Rx Day 99.

Table 4. Visit Windows for Analysis of Urinalysis

Scheduled Week	Nominal Day	Time Window (Rx Day A Range)
Week 0 DB	1 ^a	≤ 1
Week 4 DB	29	2 – 43
Week 8 DB	57	44 – 71 ^b
Week 12 OL	85	72 ^c – 112
Week 20 OL	141	113 – 161
Week 26 OL	183	162 – 190

Rx Day A = date of visit – date of first study drug injection in double-blind treatment period + 1

- a. Date of first study drug injection in double-blind treatment period.
- b. For Week 8 DB, visit window was from Rx Day 37 to Rx Day 71 or the date of the first injection in OL period (if applicable), whichever comes first.
- c. For Week 12 OL, visit window was from Rx Day 72 or the date of the first injection in OL period + 1 (if applicable), whichever comes first, to Rx Day 112.

Table 5. Visit Windows for Analysis of Fecal Calprotectin and IBDQ

Scheduled Week	Nominal Day	Time Window (Rx Day A Range)
Week 0 DB	1 ^a	≤ 1
Week 4 DB	29	2 – 43
Week 8 DB	57	44 – 71 ^b
Week 26 OL	183	72 ^c – 190

Rx Day A = date of visit – date of first study drug injection in double-blind treatment period + 1

- a. Date of first study drug injection in double-blind treatment period.
- b. Rx Day 71 or the date of the first injection in OL period (if applicable), whichever comes first.
- c. For Week 26 OL, visit window was from Rx Day 72 or the date of the first injection in OL period + 1 (if applicable), whichever comes first, to Rx Day 190.

Vital signs and laboratory measurements will also be presented on the Any Adalimumab set using the visit windows in the following tables.

Table 6. Visit Windows for Analysis of CDAI and Vital Sign (Any Adalimumab)

Visit Week	Nominal Day	Time Window (Rx Day B Range)
Week 0	1 ^a	≤ 1
Week 2	15	2 – 22
Week 4	29	23 – 36
Week 6	43	37 – 50
Week 8	57	51 – 64
Week 10	71	65 – 78
Week 12	85	79 – 92
Week 14	99	93 – 106
Week 16	113	107 – 120
Week 18	127	121 – 134
Week 20	141	135 – 148

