For all variables (discrete/categorical/response variables and continuous variables), except for the endpoint defined for dose-escalated subjects only, the following rules will be used for the LOCF approach:

1. Baseline and pre-baseline values will not be used to impute the missing post-baseline values.
2. Missing values after Study Day 1 will be imputed using the latest non-missing values after Day 1 and prior to the missing value.
3. For subjects who dose-escalate to OL adalimumab 80 mg eow, the last non-missing value before dose escalation will be used for LOCF values at the following visits.

For the endpoints defined for dose-escalated subjects only, the last non-missing value through the entire study will be used for LOCF values at the following visits.

Observed Case (OC)

Observed case analysis will be performed such that missing values will not be imputed. Data from subjects who dose-escalate to OL adalimumab 80 mg eow will be considered missing after the point of dose escalation. These data will not be imputed and will not be included in the numerator or denominator.

Imputation of Missing Dates

For baseline, efficacy, and safety parameters, if the day and/or month are missing, the following conventions will be used to impute the missing dates:

- 01 for missing start day
- End of month for missing end day
- January 1st for missing start month
- December 31st for missing end month

Rule for CDAI Calculation

Up to 14 day of diaries will be recorded in eCRF or CDAI calculation for each visit. Diary entries will be evaluated for the CDAI calculation for each visit. For each CDAI subscore, the available scores from the most recent diary days (at least 4 days, up to

7 days) prior to actual day of the study visit will be summed, and then multiplied by the corresponding multiplier to get subtotal score. If available diary entries are fewer than 7 days, the subtotal score will be calculated as (summed total available score/number of days) \times 7 \times corresponding multiplier. The three subscores (number of liquid/very soft stools, abdominal pain rating, and general well-being) will then be rounded to one decimal. The final CDAI is rounded to a whole number.

If a subject has fewer than 4 days of diary data, the total CDAI score will not be calculated and will be considered missing.

If a subject has any subscore missing, the corresponding total CDAI score will be missing.

Definition of Clinical Remission

CDAI $<$ 150.

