- Proportion of subjects who achieve CDAI $<$ 150, hs-CRP $<$ 3 mg/L and fecal calprotectin $<$ 250 μ g/g at Week 26 in subjects who achieved clinical response (decrease in CDAI \geq 70 points from Baseline) at Week 8.

Additional secondary endpoints include:

- Proportion of subjects with clinical remission (CDAI < 150) over time.
- Proportion of subjects with CDAI < 150 plus a reduction in hs-CRP of at least 50% from Baseline over time.
- Proportion of subjects with clinical response (decrease in CDAI \geq 70 points from Baseline) over time.
- Proportion of subjects with decrease in CDAI \geq 70 points from Baseline plus a reduction in hs-CRP of at least 30% from Baseline over time.
- Change from Baseline in CDAI over time.
- Change from Baseline in hs-CRP level over time.
- Change from Baseline in fecal calprotectin level over time.

The analysis over time will be performed for the DB placebo-controlled period (Week 0 to Week 4), with comparisons between active treatment and placebo groups. The analysis over time will also be performed for Any Adalimumab set (the entire study on or after the first dose of adalimumab), with only summary statistics for adalimumab treatment.

Exploratory endpoints include:

- Proportions of subjects who achieve CDAI < 150 at Week 26 in subjects who did not achieve clinical response (decrease in CDAI \geq 70 points from Baseline) at Week 8.

For categorical endpoints with comparison between the treatment groups, the difference in proportions of subjects between treatment groups will be analyzed using the CMH test adjusted for stratification variables. Additionally, the CMH based two-sided 95% confidence interval for the difference in proportions will be provided. For categorical endpoints with comparison to the clinically meaningful constant rate, the one sample Exact test will be performed and the two-sided 95% CI will be provided. The NRI imputation method will be used for subjects with missing data at the time point

evaluated. Subjects who dose-escalate will be imputed using NRI for visits after dose escalation. The LOCF method will also be used as the sensitivity analyses.

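### The SAP says its windows discard no post-baseline measurement, yet every Week 26 window closes at Day 190, and no rule says what happens to later values

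*SAP*

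**What the plan says.** SAP 6.0, Definition of Analysis Windows, opens by recognising that subjects do not keep exactly to the schedule. It says that "rules will be applied to assign actual visits to protocol-specified visits including early termination visits" and that "windows will not discard any post-baseline measurement recorded on the CRF". Where several visits fall in one window, the one closest to the target day is used.

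The tables that follow close the last window. CDAI at Week 26 has nominal Day 183 and window Day 177 to 190 (Table 2). The calprotectin and IBDQ window runs "whichever comes first, to Rx Day 190" (Table 5). No table has a later row, and no fallback is given.

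For binary endpoints, the NRI rule in SAP 6.0 is that "all missing value will be considered as 'Not Achieved". SAP 10.3 applies it to the Week 26 endpoints: "The NRI imputation method will be used for subjects with missing data at the time point" evaluated. LOCF is a sensitivity analysis: "Missing values after Study Day 1 will be imputed using the latest non-missing values after Day 1 and prior to the missing value". SAP 6.0 also plans an observed-case analysis.

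The Protocol synopsis sets the visit tolerance: "Study visits should occur within the ± 3 day visit window".

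**The concern.** A closed last window cannot satisfy a rule that nothing recorded is discarded. From Day 2 to Day 190 the tables do implement that rule, because the windows run without gaps. Only the days after 190 are uncovered.

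The endpoint exposed is clinical remission at Week 26 in Week 8 responders, together with the Week 26 key secondaries. It carries the maintenance part of the primary objective, it is open-label, and it is tested against a fixed 30%. The planned denominator is about 100 and is smaller in the steroid subsets. A recorded remission could become a failure only because the visit was late. None of the planned efficacy analyses would recover it at Week 26: NRI makes it a failure, LOCF carries forward an earlier value, and observed-case omits the subject. As the SAP stands, which rule to follow would be settled in programming, possibly after the data have been seen.

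**Working it through.** **1. The windows.** Upper limits of the Week 26 row, read from SAP 6.0:

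| Measurements | Day from first study drug | Day from first adalimumab |
|---|---|---|
| CDAI, vital signs | Table 2: 177–190 | Table 6: 177–190 |
| hs-CRP, chemistry, hematology | Table 3: 163–190 | Table 7: 163–190 |
| Urinalysis | Table 4: 162–190 | Table 8: 162–190 |
| Calprotectin, IBDQ | Table 5: 72–190 | Table 9: 72–190 |

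All eight close at Day 190.

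**2. How late a visit must be.** Nominal Week 26 is 26 × 7 + 1 = Day 183. With the ±3-day tolerance, an on-schedule visit falls on Day 180 to 186. Day 191 is 191 − 183 = 8 days after target and 191 − 186 = 5 days past the protocol limit. On the early side the windows are wider: Table 3 accepts a value 183 − 163 = 20 days early, and Table 5 one 183 − 72 = 111 days early.

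**3. Which arm.** In Tables 6 to 9 a placebo subject first given adalimumab on Day 29 reaches Week 26 at 183 − 29 + 1 = Day 155 on that clock. Day 190 there is study Day 190 + 28 = 218. In those four tables the limit therefore matters in practice only for the adalimumab arm.

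**4. The plan's own power figure.** Inputs from SAP 4.3: n = 100, null rate 30%, alternative 52%, two-sided 0.05. With X binomial(100, 0.30), P(X ≥ 39) = 0.0340 and P(X ≥ 40) = 0.0210, so 40 is the smallest count with an upper tail of at most 0.025. Power is P(X ≥ 40 | 0.52) = 0.9939, which agrees with the stated 99% or more.

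**5. Effect of losing late values.** Let f be the share of responders whose only Week 26 CDAI falls after Day 190, unrelated to outcome. The documents give no value for f, so a range is shown. The expected reported rate is 0.52 × (1 − f), and power is P(X ≥ 40) at that rate.

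| f (assumed) | Reported rate | Remitters lost per 100 | Power |
|---|---|---|---|
| 0 | 52.0% | 0 | 99.4% |
| 1% | 51.5% | 0.52 | 99.2% |
| 2% | 51.0% | 1.04 | 98.9% |
| 5% | 49.4% | 2.60 | 97.6% |
| 10% | 46.8% | 5.20 | 92.9% |

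**6. What would reverse the test.** With 52 remitters in 100, the count must fall to 39, so 52 − 39 = 13 remitters would have to be assessed only after Day 190.

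**7. What extending the CDAI window would change.** A value inside Day 177 to 190 is at most 7 days from target, and a Day 191 value is 8 days away. Under the closest-to-target rule a late CDAI never displaces an in-window one; it only fills a gap.

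**The case against.** The strongest reply is that this is a wording inconsistency with little reach, and much of that stands.

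- A reader might infer that the SAP drops late CDAIs. It never says so. The loss follows from applying the tables literally, and the no-discard sentence could equally be read as an instruction to keep the value. What the documents support is that handling is undefined.
- Few subjects are likely to be affected. The visit must be at least five days outside tolerance, with no other CDAI on Day 177 to 190. Dose-escalated subjects are already failures in the main analysis.
- A reader might infer that safety data are lost. Only the by-visit summaries are limited in this way. Shift and potentially clinically significant summaries use all values, and the final value in the Any Adalimumab set has its own limit in SAP 6.0: 70 days after the last dose, or the start of non-study adalimumab.
- A reader might infer a serious loss of power. At a true rate of 45%, power would fall from 86.6% to 82.3% (f = 2%) or 74.3% (f = 5%). But 45% appears nowhere in the documents, and f is assumed as well.
- Day 190 is target plus 7, in line with the upper reach of most other CDAI windows, and it may be deliberate. The Week 24 dose falls on 24 × 7 + 1 = Day 169, so Day 191 is already 22 days after it. A wholly open window would label values far from treatment as Week 26.

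The last point rules out an unbounded window. It does not remove the conflict: if the cut-off is deliberate, the no-discard sentence is wrong as written.

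**Conclusion.** The concern holds as a conflict between two stated rules, with the precedence left open. Under the literal reading of the tables, each remitter whose only Week 26 CDAI is on Day 191 or later costs 1 percentage point per 100 responders. With an assumed 2% to 5% affected, independently of outcome, the expected rate at a true 52% is 51.0% to 49.4%, and power is 98.9% to 97.6% instead of 99.4%.

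Counting an unmapped subject as a failure can only lower the remission rate, so the error is conservative against 30% and cannot produce a false positive. The documents do not support the reading that the choice of rule would decide the Week 26 result at the planned rate, given the 13 remitters required. The Week 4 primary endpoint is unaffected. The case for acting is that the rule should be fixed before the data are known, and that doing so is cheap.

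**What to change.** Before database lock, amend SAP 6.0 as follows.

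1. Extend the upper limit of the last window in Tables 2 to 9 so that it meets the no-discard rule. Keep the closest-to-target rule.
2. Bound it with the limit the SAP already uses for the Final Observation: within 70 days of the last dose and before any non-study adalimumab. For a last dose on Day 169 this is Day 169 + 70 = 239.
3. Report how many Week 26 values fall after Day 190, and repeat the Week 26 analyses with the Day 190 cut-off as a sensitivity analysis.

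If the sponsor intends the Day 190 cut-off, the alternative is to qualify the no-discard sentence and state that later values are treated as missing.

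The cost is SAP wording and window programming, with no new data. The downside is that a few values further from the last dose will count as Week 26. The bound also does not stop at the start of a different Crohn's therapy. The sensitivity analysis shows whether either matters.
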